### **11.2 Subject demographics and other baseline characteristics**

All data for background and demographic variables will be listed by treatment group and subject. Summary statistics will be provided by treatment group.

Relevant medical history, current medical conditions, results of laboratory screens, and any other relevant information will be listed by treatment group and subject.

### **11.3 Treatments**

Data for study drug administration (rescue medication) and concomitant therapies will be listed by treatment group and subject.

## **11.4 Analysis of the primary variable(s)**

The primary aim of the study is to compare the effect of ACZ885 versus placebo on the clinical disease activity of sarcoidosis patients as measured by the change from baseline in the percent predicted FVC at week 24.

### **11.4.1 Variable(s)**

The primary variable will be the change from baseline in percent predicted FVC after 24 weeks of treatment.

### **11.4.2 Statistical model, hypothesis, and method of analysis**

The change from baseline in percent predicted FVC will be analyzed using a Bayesian model for repeated measurements. The model will investigate effects for treatment by time (included as a class variable) interaction, baseline by time interaction and PET positivity (yes/no) prior to randomization. Uninformative priors will be utilized to obtain the posterior estimates.

The posterior probability that ACZ885 is better than placebo in terms of change from baseline in percent predicted FVC at 24 weeks will be calculated. If it is at least 90%, it will be considered a sign of efficacy of ACZ885 in increasing FVC after 24 weeks of treatment in this patient population.

At the interim analysis, the posterior probability that ACZ885 is worse than placebo in terms of change from baseline in percent predicted FVC at week 12 will be calculated. If it is at least 60%, the study may be stopped for futility.

### **11.4.3 Handling of missing values/censoring/discontinuations**

The primary analysis will consider patients with partial data (for instance without a 24 week assessment but with at least one post baseline assessment available). Estimates of the missing values will be derived by the model that are valid under the missing at random (MAR) assumption.

### **11.4.4 Sensitivity analyses**

Not applicable.

## 11.5 Analysis of secondary variable(s)

### 11.5.1 Efficacy / Pharmacodynamics

#### 11.5.1.1 [F-18]

The [F-18]FDG-PET/CT imaging data will be analyzed to identify the max standardized uptake values in the following categories:

- A maximum of 5 focal nodal uptake regions (mediastinal, hilar)
- A maximum of 5 focal regions of uptake in lung parenchyma
- A maximum of 5 extra-thoracic focal uptake regions on the whole body scan

[F-18]FDG-PET/CT mean

- A region of lung parenchyma, unaffected by focal lesion uptake

The mean of the SUVmax (resp. SUVmean) for each category will be taken to obtain one SUVmax value (resp. SUVmean) per patient / time point / category.

The mean percent change from baseline in SUVmax in the nodules after 12 weeks of treatment will be analyzed using ANCOVA with baseline SUVmax as a covariate and treatment and PET positivity (yes/no) as factors.

The same analysis as for the percent change from baseline in SUVmax in the nodules will be performed for the percent change from baseline in SUVmax in the lung parenchyma and the extra-thoracic regions, where available. It will also be repeated for SUVmean in the parenchyma.

The percentage of patients with at least 50% reduction of SUVmax in nodules will be analyzed via logistic regression with baseline SUVmax as a covariate and treatment and PET positivity (yes/no) as factors.

Also the change in the individual lung nodules will be examined, using a discretized scale of complete response (CR), partial response (PR), stable disease (SD) and progressive disease (PD) as in the oncology European Organization for Research and Treatment of Cancer criteria for [F-18]FDG-PET/CT. The proportion of individual responders and non-responders will be determined, based on PET. Patients who discontinue for lack of efficacy will be treated as a separate category in this summary.

The correlation between changes from initial FDG-PET scan in SUVmax and changes from baseline in FVC, FEV1, COAs, 6MWT distance will be assessed with graphical methods.

#### 11.5.1.2 High resolution computed tomography (HRCT)

Change in HRCT scoring from initial scan to 24 weeks will be analyzed, using a regression model with baseline HRCT score as a covariate and treatment and PET positivity (yes/no) as factors. The HRCT scans will be evaluated using an HRCT scoring system quantifying various features such as: BVB: thickening or irregularity of the bronchovascular bundle; PC: parenchymal consolidation (including ground-glass opacifications); ND: intraparenchymal nodules; LS: septal and nonseptal lines; PL: focal pleural thickening; LN: enlargement of the mediastinal lymph nodes. The score for the lung will be determined using a scoring system similar to previous published literature ([Oberstein et al 1997](#); [Ors et al 2013](#)).

In addition, HRCT results will be evaluated for worsening, improvement, or stable outcome by 2 blinded assessors in side-by-side comparison. Results will be summarized in a shift table.

Corporate Confidential Information

#### **11.5.1.3 Other secondary variables**

Data from other pulmonary function tests and 6MWT will be listed and summarized. Graphical representations of the pulmonary function test endpoints over time will be presented.

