### 2.2 Secondary objectives

Secondary objectives	Endpoints related to secondary objectives

To determine the effect of ACZ885 on decreasing the maximum standardized uptake value (SUVmax) [F-18]FDG-PET in nodules (nodular uptake regions) after 12 weeks of treatment, compared to placebo.

	

Percent change from initial scan in [F-18]FDG-PET SUVmax at week 12

To determine the effect of ACZ885 versus placebo on other parameters of pulmonary function testing (i.e., absolute FVC, FEV1, FEV1/FVC, FEV3, FEF25-75, FEV3/FVC, FEV6, TLC, RV, RV/TLC, DLco and post-bronchodilator FEV1/reversibility) in patients with sarcoidosis at 24 weeks compared to baseline

	

Lung function testing results at 24 weeks compared to baseline

To determine the effect of ACZ885 versus placebo on HRCT of patients with sarcoidosis at 24 weeks compared to initial HRCT scan as measured by side-by-side comparison by blinded reviewers and HRCT scoring

	

HRCT results at 24 weeks compared to HRCT initial scan measured by blinded reviewers and HRCT scoring

To determine the effect of ACZ885 versus placebo on the 6-minute walk test (6MWT) distance of patients with sarcoidosis at 12 and 24 weeks compared to baseline

	

6MWT results at week 12 and 24 compared to baseline

Secondary objectives	Endpoints related to secondary objectives

• To determine the effect of ACZ885 on additional [F-18]FDG-PET outcomes (i.e., SUVmean, SUVpeak and volume of the lesions) after 12 weeks of treatment compared to placebo

	

• Percent change from initial scan in additional [F-18]FDG PET outcomes at week 12

• To assess the safety and tolerability of ACZ885 in patients with sarcoidosis as measured by adverse events (AEs)

	

• Adverse events in patients taking ACZ885 compared to placebo

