## **6.2 Secondary objectives**

### **6.2.1 Variables**

Secondary variables for this study are:

- [F-18]FDG-PET/CT
- HRCT
- Pulmonary function tests: Change from baseline in absolute and % predicted FVC, FEV1, FEF25-75, FEV1/FVC, FEV3, FEV3/FVC, FEV6, TLC, RV, RV/TLC, DLCO, and post-bronchodilator FEV1/reversibility and other parameters as needed
- 6MWT outcomes: Change from baseline in distance, oxygen saturation, hearth rate and Borg Questionnaire score

For the pulmonary function test parameters the direction of benefit is as follows

- an increase in values is beneficial: absolute and % predicted FVC, FEV1, FEF25-75, FEV1/FVC, FEV3, FEV6, FEV3/FVC, DLCO
- a decrease in values is beneficial: RV, TCL, RV/TCL.

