### **6.2.2 Descriptive analyses**

All secondary variables will be listed by treatment, subject and visit/time. Descriptive statistics will be provided by treatment and visit/time for all continuous variables. Summary statistics will include arithmetic mean, SD, CV (arithmetic), median, minimum and maximum. Graphical methods will be employed to show mean (SD) figures for raw or derived value (such as change from baseline or percent change from baseline) for each endpoint.

Incidences of patients with complete response (CR), partial response (PR), stable disease (SD) and progressive disease (PD) will be summarized by treatment group over time, patients who discontinue for lack of efficacy will be treated as a separate category in this summary. The best response by subject will also be summarized by treatment group; CR is the best possible response and will supersede any previous response of PR or SD. PR will supersede SD. If a subject has a response of PD this is the only best response they can have.

The correlation between changes from initial FDG-PET scan in SUVmax and changes from baseline in FVC, FEV1, PROs, 6MWT distance will be assessed with scatterplot grids. As we may not be able to assume normality of the data, Kendall's tau-b coefficients and its corresponding p-values will be displayed to assess correlation.

Summary stats by PET positivity will be provided for the analyses on:

- PET data
- HRCT total scores
- 6MWT
- FEV1,FEV3,FEV6 (L as well as % of predicted)

Data on new lesions from [F-18]FDG-PET/CT will be only listed.

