### **Key Pulmonary function tests (FEV1, FEV3 and FEV6)**

FEV1, FEV3 and FEV6 (both in liters and percent as units) will be analyzed using the same analysis as defined in Section 6.1.3 but under a frequentist approach (no prior will be applied). The same sensitivity and subgroup analyses as the primary may also be performed, if deemed necessary.

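### The 6MWT objective compares ACZ885 with placebo, but the plan only summarises 6MWT by arm and produces no between-arm difference or interval

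*Protocol*

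**What the plan says.** Protocol 2.2 lists 6MWT as a separate secondary objective: "To determine the effect of ACZ885 versus placebo on the 6-minute walk test (6MWT) distance of patients with sarcoidosis at 12 and 24 weeks". The paired endpoint is "6MWT results at week 12 and 24 compared to baseline". SAP 1.3.2 repeats both.

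The analysis sections treat it as follows.

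- Protocol 11.5.1.3: "Data from other pulmonary function tests and 6MWT will be listed and summarized". The graphs mentioned there are for the pulmonary function tests.
- SAP 6.2.1 defines the variable: "6MWT outcomes: Change from baseline in distance, oxygen saturation", with heart rate and Borg score also named.
- SAP 6.2.2: "Descriptive statistics will be provided by treatment and visit/time for all continuous variables". These are mean, SD, CV, median, minimum and maximum, with plots of mean (SD).
- SAP 6.2.2 uses 6MWT in two other ways. It is on the list introduced by "Summary stats by PET positivity will be provided for the analyses on", and its change is correlated with SUVmax change (Kendall's tau-b). Neither contrasts the arms.
- SAP 6.2.3 specifies models with a treatment term for PET and HRCT. For lung function it says "FEV1, FEV3 and FEV6 (both in liters and percent as units) will be analyzed using the same analysis as defined in Section 6.1.3", in a frequentist version. 6MWT does not appear.

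Missing-data handling (missing at random, optional LOCF) is described in Protocol 11.4.3 and SAP 6.1.3 and 6.1.5 for the primary endpoint. No rule is stated for 6MWT.

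**The concern.** The objective asks a comparative question and the written analysis does not answer it. The output is two columns of summary statistics, with no estimate of the difference between arms and no statement of its uncertainty. In a proof-of-concept study meant to guide further development, that estimate is what the 6MWT objective asks for.

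The SAP itself makes the omission visible. Protocol 11.5.1.3 puts 6MWT and the other pulmonary function tests under one descriptive sentence. The SAP then moves FEV1, FEV3 and FEV6 to a repeated-measures model and leaves 6MWT behind without giving a reason. Yet 6MWT has its own objective, while the FEV measures share one with many other lung function parameters.

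A second, smaller point is missing data. Some patients will have a Week 12 walk and no Week 24 walk. A repeated-measures model uses the Week 12 value, and a plain Week 24 mean does not.

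**Working it through.** **1. Is there a between-arm 6MWT analysis anywhere?** The sections above are the only readable ones that deal with analysing 6MWT, and none gives a treatment difference, interval, test or posterior probability. Redaction is an unlikely explanation. SAP 6.2.3, where the secondary models sit, shows none. The redacted SAP text lies in first results, interim, part of 6.1.3, primary supportive, pharmacokinetic, exploratory and biomarker sections.

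**2. The plan's own figure.** No power or precision is stated for 6MWT (Protocol 11.8: not applicable). The only figure is for the primary endpoint in Protocol 11.7: 15 per arm, SD 9, difference 7, 10% one-sided error, about 80% power. It reproduces: 7 / (9 × √(2/15)) = 2.130; 2.130 − 1.282 = 0.849; power = 80.2% (79.3% with the t distribution). I borrow only the 15 per arm from it.

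**3. Precision of the missing estimate.** The documents give no SD for 6MWT, so the unit is the SD of change.

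- SE = √(2/15) = 0.365 SD. The 90% half-width is 1.701 × 0.365 = 0.62 SD (t, 28 df).
- With all 19 per arm contributing: 1.688 × √(2/19) = 0.55 SD.
- For an assumed SD of 40, 60, 80 or 100 m, 0.62 SD is about 25, 37, 50 or 62 m.
- Baseline adjustment multiplies the variance by (1 + ρ)/2, assuming equal variances at baseline and follow-up. That is 0.75 at ρ = 0.5 and 0.95 at ρ = 0.9, so the half-width falls to about 0.62 × √0.75 = 0.54 or 0.62 × √0.95 = 0.60 SD.

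**4. Possible bias in raw Week 24 means.** Protocol 3.1 plans 38 randomised and 30 completers, so 8/38 = 21% are allowed for as losses. SAP Table 4-1 also removes PD data after prohibited medication.

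Assumptions: a true difference of 0.5 SD; dropout follows a logistic model in the standardised Week 12 change Z, with worse walkers leaving more often; losses are 2/19 = 11% on ACZ885 and 6/19 = 32% on placebo; r is the correlation between Week 12 and Week 24 change. Then:

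observed-case difference = 0.5 + r × (mean Z of stayers on ACZ885 − mean Z of stayers on placebo)

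| Dropout slope per SD (odds ratio) | Stayer difference in Z | r = 0.5 | r = 0.7 | r = 0.8 |
|---|---|---|---|---|
| 0.25 (1.3) | −0.051 | 0.47 | 0.46 | 0.46 |
| 0.5 (1.6) | −0.099 | 0.45 | 0.43 | 0.42 |
| 1.5 (4.5) | −0.215 | 0.39 | 0.35 | 0.33 |

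The bias is about 0.03 to 0.17 SD, here against ACZ885. Reversing the split reverses the sign. Equal dropout with the same slope in both arms gives no bias. Conditioning on Week 12 restores 0.50, because in this example dropout depends only on Week 12.

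**The case against.** **Side-by-side summaries already allow a comparison.** This stands in part. The trial is randomised and blinded, placebo values sit beside active values, and an unadjusted difference follows from the means and SDs once the numbers of patients are shown. So it would be too strong to infer that no comparison is possible. What is missing is a planned estimate with an interval, baseline adjustment and use of partial data.

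**The tiering looks deliberate.** The SAP models PET, HRCT and what it labels key pulmonary function tests, and describes the rest. The protocol's rationale says 6MWT has had limited use in sarcoidosis and needs careful interpretation. The study is non-confirmatory, and its efficacy criterion uses FVC alone. This limits the importance of the point, but the objective is still worded as a comparison.

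**Little would be learned from so wide an interval.** The interval is wide, but reporting it shows that imprecision, which arm means alone leave unstated.

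**The gain from repeated measures is smaller than for spirometry.** This is fair. The objective names only Weeks 12 and 24, the 6MWT row of the assessment schedule is not readable in this copy, and the gain from baseline adjustment is modest.

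**The same sentence covers DLco, TLC, RV and FEF25-75.** This is correct. They fall under a similarly comparative objective and also have no model. 6MWT is singled out because it has an objective of its own.

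**Two stronger readings go too far.** A reader might infer an inflated false-positive rate from judging each arm's change separately, but the plan contains no within-arm test of 6MWT. A reader might also infer that the plan prescribes observed-case means and that they are biased. The plan states no missing-data rule for 6MWT. Use of available cases is a presumption, the 8 losses are a recruitment allowance, and Protocol 7.2 says that stopping treatment is not automatically withdrawal from the study.

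**Conclusion.** The mismatch is real. Followed as written, the plan produces no ACZ885-minus-placebo difference in 6MWT distance and no interval for it, although a secondary objective asks for the effect against placebo at two time points. The change is worth making because it is cheap.

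The statistical loss is moderate and partly hypothetical. The half-width of about 0.62 SD rests on 15 patients per arm with no baseline adjustment. The 0.03 to 0.17 SD bias rests on an assumed 11%/32% split, slopes of 0.25 to 1.5 and correlations of 0.5 to 0.8. It shows what could happen, not what to expect. If dropout depended on unobserved Week 24 performance, the repeated-measures model would not fully remove the bias either.

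Nothing here bears on the FVC analysis, its power, the sample size or the 90% posterior-probability criterion.

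**What to change.** In SAP 6.2.3, add change from baseline in 6MWT distance to the endpoints analysed with the frequentist repeated-measures model used for FEV1/FEV3/FEV6. Include treatment by visit and baseline distance by visit, and use the visits at which 6MWT is done. Report the ACZ885-minus-placebo difference with a 90% interval at Weeks 12 and 24. The 90% level matches the credibility intervals planned in SAP 6.1.3.1. Label the result supportive, attach no success criterion, state that the model assumes missing at random, and keep the descriptive tables. Align the 6MWT wording in Protocol 11.5.1.3.

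If the sponsor wants description only, the alternative is to reword the objective in Protocol 2.2 and SAP 1.3.2. The same choice should be made openly for DLco, lung volumes and the other lung function measures without a model.

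The cost is a few lines of text and one more run of a model already planned, with no new data or patients. The downsides are one more secondary comparison without multiplicity control, acceptable in a study that calls itself non-confirmatory, and an interval that will probably be too wide to settle the question.

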### **11.5.2 Safety**

#### **11.5.2.1 Vital signs**

All vital signs data will be listed by treatment, subject, and visit and if ranges are available abnormalities (and relevant orthostatic changes) will be flagged. Summary statistics will be provided by treatment and visit.

#### **11.5.2.2 ECG evaluations**

All ECG data will be listed by treatment, subject and visit/time, abnormalities will be flagged. Summary statistics will be provided by treatment and visit.

#### **11.5.2.3 Clinical laboratory evaluations**

All laboratory data will be listed by treatment, subject, and visit/time and if normal ranges are available abnormalities will be flagged. Summary statistics will be provided by treatment and visit/time.

#### **11.5.2.4 Adverse events**

All information obtained on adverse events will be displayed by treatment and subject. The number and percentage of subjects with adverse events will be tabulated by body system and preferred term with a breakdown by treatment. A subject with multiple adverse events within a body system is only counted once towards the total of this body system.

### **11.5.3 Pharmacokinetics**

Corporate Confidential Information

#### **11.5.4 Pharmacokinetic/pharmacodynamic interactions**

The relationship between PK and efficacy/PD parameters may be investigated using graphical methods and simple regression models.

#### **11.5.5 Other assessments**

Not applicable.

### **11.6 Analysis of exploratory variables**

Statistical analysis for exploratory variables will be described in the statistical analysis plan.

#### **11.6.1 Exploratory biomarkers**

Corporate Confidential Information

### **11.7 Sample size calculation**

The sample size is determined by calculations with respect to the Bayesian analyses ([Fisch et al 2014](#)) (based on uninformative priors) of the change from baseline in the percent predicted FVC after 24 weeks of treatment. With 15 patients per group providing data at week 24 and assuming a standard deviation of 9% ([Judson et al 2014](#)), there is approximately 80% power to meet the efficacy criterion, if the true effect of ACZ885 over placebo is 7%.

Under the same assumption for the standard deviation, there is 10% probability of meeting the efficacy criterion if the true treatment difference is 0% (type I error rate).

## **11.8 Power for analysis of key secondary variables**

Not applicable.

## **11.9 Interim analyses**

Corporate Confidential Information

# **12 Ethical considerations**

## **12.1 Regulatory and ethical compliance**

This clinical study was designed and shall be implemented, executed and reported in accordance with the ICH Harmonized Tripartite Guidelines for Good Clinical Practice, with applicable local regulations (including European Directive 2001/20/EC, US Code of Federal Regulations Title 21, and Japanese Ministry of Health, Labor, and Welfare), and with the ethical principles laid down in the Declaration of Helsinki.

## **12.2 Responsibilities of the investigator and IRB/IEC**

Before initiating a trial, the investigator/institution must obtain approval/favorable opinion from the Institutional Review Board/Independent Ethics Committee (IRB/IEC) for the trial protocol, written informed consent form, consent form updates, subject recruitment procedures (e.g., advertisements) and any other written information to be provided to subjects. Prior to study start, the investigator is required to sign a protocol signature page confirming

his/her agreement to conduct the study in accordance with these documents and all of the instructions and procedures found in this protocol and to give access to all relevant data and records to Novartis monitors, auditors, Novartis Quality Assurance representatives, designated agents of Novartis, IRBs/IECs, and regulatory authorities as required. If an inspection of the clinical site is requested by a regulatory authority, the investigator must inform Novartis immediately that this request has been made.

For multi-center trials, a Coordinating Investigator will be selected by Novartis around the time of Last Patient Last Visit to be a reviewer and signatory for the clinical study report.

### **12.3 Publication of study protocol and results**

The key design elements of this protocol will be posted in a publicly accessible database such as clinicaltrials.gov. In addition, upon study completion and finalization of the study report the results of this trial will be either submitted for publication and/or posted in a publicly accessible database of clinical trial results.

## **13 Protocol adherence**

This protocol defines the study objectives, the study procedures and the data to be collected on study participants. Additional assessments required to ensure safety of subjects should be administered as deemed necessary on a case by case basis. Under no circumstances is an investigator allowed to collect additional data or conduct any additional procedures for any research related purpose involving any investigational drugs under the protocol.

Investigators ascertain they will apply due diligence to avoid protocol deviations. If an investigator feels a protocol deviation would improve the conduct of the study this must be considered a protocol amendment, and unless such an amendment is agreed upon by Novartis and approved by the IRB/IEC/REB it cannot be implemented.

